4.3.1.5 Healthcare Resource Utilization

Healthcare resource utilization will be collected by the investigator or designee at each study visit after randomization and will be recorded on the eCRF.

4.3.2 Patient Reported Outcomes

Subjects will receive an ePRO device and a hand-held spirometer at Visit 2 (Week -4) to be used for completion of PRO assessments (ie, Asthma Daily Diary, ACQ-6, AQLQ[S]+12, WPAI+CIQ, EQ-5D-5L) and home peak flow testing. The study center staff will be trained on how to use the devices and will be responsible for instructing subjects on how to use both devices. Subjects will have an opportunity to practice using the devices through a preprogrammed training module. Subjects should be informed that the recordings made electronically cannot be retrospectively or prospectively entered and must be completed within a defined time window. Subjects will also be provided with information about when and where to request help if problems occur.

Subjects must bring the ePRO device to each study visit, and compliance with all PRO assessments and home peak flow testing will be checked by center staff.

4.3.2.1 Asthma Daily Diary

The Asthma Daily Diary includes the following daily assessments: asthma symptoms; inhalations of rescue medication; nighttime awakening due to asthma requiring rescue medication use, asthma-related activity limitations, asthma-related stress, and background medication compliance.

The Asthma Daily Dairy will be completed each morning and evening. There will be triggers in the ePRO device to alert the subjects to signs of worsening of asthma and to contact the investigator (see Section 4.3.1).

4.3.2.2 Asthma Control Questionnaire-6

The ACQ is a patient-reported questionnaire assessing asthma symptoms (ie, night-time waking, symptoms on waking, activity limitation, shortness of breath, wheezing) and daily rescue bronchodilator use and FEV₁ (Juniper et al, Oct 1999). The ACQ-6 is a shortened version of the ACQ that omits the FEV₁ measurement from the original ACQ score. Questions are weighted equally and scored from 0 (totally controlled) to 6 (severely uncontrolled). The mean ACQ score is the mean of the responses. Mean scores of \leq 0.75 indicate well-controlled asthma, scores between 0.75 and \leq 1.5 indicate partly-controlled asthma, and a score > 1.5 indicates uncontrolled asthma (Juniper et al, 2006). Individual changes of at least 0.5 are considered to be clinically meaningful (Juniper et al, 2005).

The study center staff will provide initial training on the ePRO device at Visit 1 (Week -5) in order for the subject to complete the screening ACQ-6 at the study center. The ePRO device will remain at the study center until Visit 2 (Week -4).

At Visit 2 (Week -4), study center staff will provide training as described in Section 4.3.2 and will give the subject the ePRO device to take home. The subject will complete the ACQ-6 weekly during the Screening/Run-in period. The Visit 2 (Week -4), Visit 3 (Week -1), and Visit 4 (Week 0, Day 1) ACQ-6 will be completed at the study site on the ePRO device. Subjects will be prompted to complete the ACQ-6 at Week -3 and Week -2 at home on the ePRO device. Once randomized, subjects will be prompted to complete the ACQ-6 every 2 weeks at home on the ePRO device through Week 64.

Subjects must have an ACQ-6 score of ≥ 1.5 twice during screening. The first time must be at Visit 1 (Week -5). If the ACQ-6 score is not ≥ 1.5 at Visit 1 (Week -5), then the subject should not continue in the study (screen failure). The second time the subject must have an ACQ-6 score of ≥ 1.5 may be at either Week -2 (at home on the electronic patient-reported outcome [ePRO] device) or at Visit 3 (Week -1).

4.3.2.3 Asthma Quality of Life Questionnaire, Standardised (AQLQ[S])+12

The AQLQ(S)+12 is a 32-item questionnaire that measures the HRQoL experienced by asthma patients (Juniper et al, May 1999). The questionnaire comprises 4 separate domains (symptoms, activity limitations, emotional function, and environmental stimuli). Subjects are asked to recall their experiences during the previous 2 weeks and to score each of the 32 questions on a 7-point scale ranging from 7 (no impairment) to 1 (severe impairment). The overall score is calculated as the mean response to all questions. The 4 individual domain scores (symptoms, activity limitations, emotional function, and environmental stimuli) are the means of the responses to the questions in each of the domains. Individual improvement in both the overall score and individual domain scores of 0.5 has been identified as a minimally important change, with score changes of \geq 1.5 identified as large meaningful changes (Juniper et al, 1994).

The questionnaire will initially be completed at the study center on Visit 4 (Week 0, Day 1) on the ePRO device. Subjects will then be prompted to complete the AQLQ(S)+12 every 4 weeks at home on the ePRO device through Week 64.

4.3.2.4 Work Productivity and Activity Impairment Questionnaire plus Classroom Impairment Questions (WPAI+CIQ)

The WPAI+CIQ will be used to measure self-reported productivity loss and consists of questions about how asthma and asthma-related issues impact the subject's ability to work, attend class, and perform regular activities of daily living within the previous 7 days.

The questionnaire will initially be completed at the study center on Visit 4 (Week 0, Day 1) on the ePRO device. Subjects will then be prompted to complete the WPAI+CIQ every 2 weeks at home on the ePRO device through Week 52.

4.3.2.5 EQ-5D-5L European Quality of Life-5 Dimensions, 5 Level Version

The EQ-5D-5L questionnaire assesses 5 dimensions: mobility, self-care, usual activities, pain/discomfort, and anxiety/depression. Each dimension has 5 response options (no problems, slight problems, moderate problems, severe problems, and extreme problems) that reflect increasing levels of difficulty.

The subject will be asked to indicate his/her current health state by selecting the most appropriate level in each of the 5 dimensions. The questionnaire also includes a visual analogue scale, where the subject will be asked to rate current health status on a scale of 0-100, with 0 being the worst imaginable health state.

The questionnaire will initially be completed at the study center on Visit 4 (Week 0, Day 1) on the ePRO device. Subjects will then be prompted to complete the EQ-5D-5L weekly at home on the ePRO device through Week 52.

4.3.3 Medical History and Physical Examination, Electrocardiogram, Weight, and Vital Signs

4.3.3.1 Medical and Asthma History

Complete medical history will include history and current medical conditions, past or present cardiovascular disorders, respiratory, gastrointestinal, renal, hepatic, neurological, endocrine, lymphatic, hematologic, immunologic, dermatological, psychiatric, genitourinary, drug and surgical history, or any other diseases or disorders.

The asthma history questionnaire, also completed as part of the screening evaluations, includes questions related to the subject's asthma history, duration of asthma, asthma medications, and number of exacerbations/hospitalizations and treatments in the previous 12 months.

4.3.3.2 Physical Examination Weight, Height

Physical examinations, including weight will be performed by a physician or qualified designee and will include examination of the following: general appearance, head, ears, eyes, nose, throat, neck, skin, cardiovascular system, respiratory system, abdominal system, and nervous system. Medically significant changes from the screening physical examination will be considered AEs and recorded as such on the collection instrument provided.

Height will be measured at Visit 1 (Week -5) only.

4.3.3.3 Vital Signs

Vital signs (blood pressure, temperature, pulse rate, and respiration rate) will be obtained before investigational product administration on all treatment days. After investigational product administration, subjects will be monitored for immediate drug reactions; vital signs will be taken 60 and 120 minutes (\pm 5 minutes) after the first 5 doses of investigational product are administered, and 60 minutes (\pm 5 minutes) after the sixth and subsequent doses of investigational product are administered. If the subject is not stable, vital signs should be monitored at least hourly until the subject is discharged from the study center.

Vital signs (blood pressure, temperature, pulse rate, and respiration rate) will be obtained at each visit after the subject has been resting for at least 5 minutes. Subjects should be seated and pulse rate will be measured before blood pressure.

4.3.3.4 Electrocardiogram

In a Phase 1 study with healthy subjects, no effects of MEDI9929 were observed in cardiac electrophysiological intervals. An ECG sub-study will be performed in this study to confirm that MEDI9929 does not affect QT/QTc intervals in the target population of patients with inadequately controlled, severe asthma. Approximately 160 subjects will take part in the substudy. The size of this subset will allow for characterization of QT/QTc effects and further support the safety profile of MEDI9929 with respect to QT/QTc and other ECG data.

Computerized triplicate 12-lead ECG recordings will be obtained as part of the ECG sub-study from all subjects until the approximately 40 subjects in each treatment arm have completed the study, and will be transmitted to a central reader to quantitatively assess PR, QRS, QT, and QTc intervals.

Once there are sufficient data for the sub-study, the sponsor or designee will communicate this to all participating study sites, and from that timepoint on, only one 12-lead ECG recording will be obtained, and the ECGs tracings will not be transmitted to a central reader.

The ECG assessments will be performed in accordance with the schedule of study procedures, at the same time of day and prior to blood drawing, FE_{NO} , spirometry, and administration of investigational product. The same ECG machine is to be used for the assessment throughout the subject's participation in the study.

The subjects should be instructed to refrain from taking their usual asthma controller medication (see Table 4.3.3.4-1) prior to scheduled ECG assessment. The medication restriction is waived for the screening ECG at Visit 1 (Week -5).

Table 4.3.3.4-1 Prohibited Medications and Minimum Time Intervals Prior to Electrocardiogram Testing

Concomitant Medication	Minimum Time Interval from Last Medication Dose to ECG Testing
Short-acting bronchodilators (eg, SABA [albuterol/salbutamol]), short acting anti-cholinergics (eg, ipratropium)	6 hours
Long-acting bronchodilators (eg, LABA, LAMA)	12 hours

ECG = electrocardiogram; LABA = long-acting $\beta 2$ agonist; LAMA = long-acting anti-muscarinics; SABA = short-acting $\beta 2$ agonist

Template 16.0

The ECGs will begin after the subject has been supine for at least 10 minutes. Each tracing will be separated by approximately 1 minute. Each lead will be recorded for at least 3-5 beats at a speed of 25 mm/second paper speed and 10 mm/mV amplitude. Heart rate, PR, QRS, QT and QTc intervals (millisecond) will be recorded from the 12-lead ECG.

The principal investigator or a designated subinvestigator will be responsible for the overall interpretation and determination of clinical significance of any potential ECG findings. Printouts of the ECG will be signed, dated, and stored at the study center with the subject's source documents. In addition, ECG data and evaluations (eg, clinical significance) will be recorded in the eCRF. Further details on recording computerized ECG recordings will be provided in a separate manual.

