- High blood eosinophil count ($\geq 250 \text{ cells/}\mu\text{L}$) and high ICS dose level
- Low blood eosinophil count (< 250 cells/μL) and medium ICS dose level
- Low blood eosinophil count (< 250 cells/μL) and high ICS dose level

At least 50% of the total subjects will be enrolled in the high blood eosinophil stratum ($\geq 250 \text{ cells/}\mu\text{L}$), and at least 40% of the subjects in each blood eosinophil stratum will be receiving high-dose ICS. Once the required number of subjects has been enrolled into a stratum, any subjects already in screening/run-in may be enrolled into that stratum if eligible. The stratum will then be closed, and no further subjects will be enrolled into it.

[figure not shown]
After stratification, subjects will be randomized in a 1:1:1:1 ratio to receive one of 3 dose levels of SC MEDI9929 (280 mg Q2W, 210 mg Q4W, or 70 mg Q4W) or placebo Q2W for 52 weeks (Figure 3.1.1-1). In the event that enrollment of the Japanese subjects is delayed, non-Japanese sites may be permitted to continue to enroll subjects to reach the required sample size for the Stage I analysis (see Section 4.8.7). In this event, the overall number of subjects in the study will increase in order for sites in Japan to meet the 15% Japanese enrollment goal. After the required number of subjects have been enrolled for the Stage I analysis, the requirement for stratification by medium- or high-dose ICS will be removed in order to facilitate enrollment of the remainder of the Japanese subjects into the study.

There will be an interim analysis after approximately 552 subjects have completed the Week 28 visit. The objective of this interim analysis is to accelerate decisions on future development options for MEDI9929. No futility analysis is planned and no statistical inference will be made from the interim analysis results. Regardless of the interim analysis results, the study will be continued and completed. Maintaining stable background therapy until the end of the treatment period will prevent any independent confounding variables on the treatment effect of MEDI9929. Continuing stable background therapy through Week 64

will permit duration of response analysis after the last dose of MEDI9929 in order to determine the dose-regimen for future studies.

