An ECG sub-study will be done in subgroup of subjects to confirm that MEDI9929 does not affect cardiac electrophysiological intervals. Additionally, flow cytometry will be performed at selected sites to evaluate intracellular cytokines in T cells by flow cytometry following *ex vivo* stimulation by phorbol myristate acetate.

Subjects will be in this study for approximately 1.3 years (69 weeks), which includes a screening/run-in period of up to approximately 5 weeks, a 52-week treatment period, and a 12-week post-treatment follow-up period. The last dose of investigational product will be administered at Week 50.

Investigational Product administered to all subjects Q2W

Figure 3.1.1-1 Study Flow Diagram

BD = bronchodilator; EOS = eosinophils; FEV₁ = forced expiratory volume in 1 second; ICS = inhaled corticosteroids; N = number of subjects per treatment group; Q2W = every 2 weeks; Q4W = every 4 weeks, SC = subcutaneous

Note: Every subject receives 3 injections of investigational product Q2W (subjects receiving MEDI9929 Q4W will receive placebo on alternate weeks in order to maintain the blind) in the study. All subjects will be on background asthma therapy of medium- or high-dose ICS and LABA with or without additional asthma controller medications (LTRA, LAMA, cromones, theophylline, and/or maintenance OCS) from screening through the follow-up period.

The endpoints to be measured in this study are described in Section 2.2.

^{*} Current post-BD FEV $_1$ reversibility is defined as post-BD change in FEV $_1$ of $\geq 12\%$ and ≥ 200 mL at one of the screening visits

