4.8.5.3 Analysis of Electrocardiograms

The number of subjects with clinically significant abnormal ECG results based on investigators' judgments will be summarized by treatment group and visit for all subjects.

For the ECG sub-study (approximately 160 subjects), the 12-lead ECG results, QTc intervals (millisecond), will be summarized descriptively by treatment group and visit. Changes from baseline will be summarized into 3 categories: increase \leq 30 millisecond, 30 millisecond < increase \leq 60 millisecond, and increase > 60 millisecond by treatment group and visit. On Day 1, ECGs will be performed in triplicate; the average of these 3 reads will be used as baseline value. Shift tables for QTc intervals (QTc \leq 450 millisecond, 450 < QTc \leq 480 millisecond, 480 millisecond < QTc \leq 500 millisecond, QTc > 500 millisecond) will be presented to compare the baseline ECG evaluation and the post-dose evaluations.

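### The ECG sub-study is meant to confirm that there is no QT/QTc effect, but Section 4.8.5.3 plans no placebo-corrected estimate or confidence bound that could confirm it

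*Protocol*

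**What the plan says.** The aim appears in the synopsis (Study Design), in Section 3.1.1 ("to confirm that MEDI9929 does not affect cardiac electrophysiological intervals") and in Section 4.3.3.4 ("An ECG sub-study will be performed in this study to confirm that MEDI9929 does not affect QT/QTc intervals in the target population"). All three describe a conclusion of no effect.

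On size, Section 4.3.3.4 says "Approximately 160 subjects will take part in the substudy". Triplicate, centrally read ECGs continue in all subjects "until the approximately 40 subjects in each treatment arm have completed the study". The size is justified only in words: "The size of this subset will allow for characterization of QT/QTc effects and further support the safety profile of MEDI9929".

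On analysis, Section 4.8.5.3 says of the sub-study that "the 12-lead ECG results, QTc intervals (millisecond), will be summarized descriptively by treatment group and visit". It adds counts of subjects by size of increase (up to 30 ms, above 30 to 60 ms, above 60 ms) and shift tables with cut points at 450, 480 and 500 ms. The baseline is the mean of the Day 1 triplicate. Section 4.8.5 has ECG changes from baseline evaluated in the active and placebo groups and summarized descriptively. Under Section 4.8.1 such summaries include the mean and SD.

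**The concern.** An aim of confirming no effect needs a statement of how large an effect the data rule out. The planned displays do not provide one. They show each arm's own change, but they do not estimate the difference from placebo, bound it, or say which result would count as confirmation and which would not. As written, the only route to confirmation is that nothing in the tables stands out, and that route has no defined error rate.

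At stake is the strength of a safety statement. A modest mean QTc prolongation could be present while the tables look unremarkable. Yet the data to be collected (randomized arms, concurrent placebo, triplicates, central reading) could support a properly bounded statement.

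**Working it through.** **Inputs.** From the protocol: about 40 per arm in four arms (Section 4.3.3.4), 1:1:1:1 allocation (Section 3.1.1), ECGs at Weeks 12, 20, 28, 40 and 52 (Tables 4.2.2-1 and 4.2.2-2), and the dosing weeks in Table 3.1.2-1. Assumptions, because the protocol gives no figure: SD of QTc change 10, 15 or 20 ms; true mean shifts of 5 and 10 ms; an illustrative margin of 10 ms.

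**1. The plan's own figure.** 4 × 40 = 160, which reproduces. With no SD, margin, alpha or power stated for QTc, 40 per arm cannot be derived any further.

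**2. Precision of the contrast that is not planned.** SE = SD × √(2/40) = 0.2236 × SD. The two-sided 90% CI half-width is 1.645 × SE.

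| | SD 10 | SD 15 | SD 20 |
|---|---|---|---|
| SE (ms) | 2.24 | 3.35 | 4.47 |
| 90% CI half-width (ms) | 3.7 | 5.5 | 7.4 |
| True 5 ms shift missed, two-sided 0.05 t test | 40% | 69% | 80% |
| True 10 ms shift missed, same test | 1% | 16% | 40% |

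The last two rows use the noncentral t distribution at 40 versus 40. They describe a formal test, which the protocol does not plan, and are given only for scale.

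**3. What the category tables can show.** With normal changes, the expected number of 40 subjects above 30 ms is 40 × [1 − Φ((30 − mean)/SD)].
- Mean shift 10 ms: 40 × 0.0228 = 0.9 (SD 10), 40 × 0.0912 = 3.6 (SD 15), 40 × 0.1587 = 6.3 (SD 20).
- Mean shift 0: 0.05, 0.9 and 2.7.

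A 10 ms mean shift therefore adds only about one to four subjects to that count. An empty category is weak evidence too: 0 of 40 is compatible with a true rate of up to 1 − 0.05^(1/40) = 7.2% (one-sided 95%).

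**4. What a bound would deliver.** For one dose at one visit with the illustrative 10 ms margin, the chance that the upper bound falls below the margin is Φ((10 − true effect)/SE − 1.645).
- True effect 0: 0.998, 0.91 and 0.72 (SD 10, 15, 20).
- True effect 3 ms: 0.93, 0.67 and 0.47.
- True effect 10 ms: 0.05 at any SD.

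These probabilities belong to a single estimate. If the bound had to clear the margin at all five visits, then with an assumed between-visit correlation of 0.5 a drug with no effect would pass with probability about 0.99, 0.73 and 0.40. An average over the five visits has SE multiplied by √((1 + 4 × 0.5)/5) = 0.775. That gives half-widths of about 2.8, 4.3 and 5.7 ms, and pass probabilities above 0.99, about 0.99 and 0.89.

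**5. Timing of the ECGs.** In both Q4W arms, active doses fall at Weeks 0, 4, …, 48. Weeks 12, 20, 28, 40 and 52 are therefore each nominally four weeks after an active dose, since ECGs precede dosing and no dose is given at Week 52. In the Q2W arm they are nominally two weeks after the previous dose. The tables describe trough exposure.

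**The case against.** The strongest reply is that this is only a wording mismatch. Section 4.3.3.4 itself says the subset allows characterization of QT/QTc effects, and a descriptive plan suits that. A model, interval and margin for QTc could properly sit in a SAP, which is not shown, and nothing in Section 4.8.5.3 forbids them. No confirmatory QT hypothesis is listed: in Section 2.2.2 ECG is one item among the safety endpoints. Section 4.8.6 also allows an exposure–safety evaluation, though only as an option and not specifically for QTc.

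Much of this stands. The absence of a model from the protocol is not the finding. The finding is that the protocol states an aim of confirmation and fixes beside it an analysis that cannot deliver one. A SAP could add the contrast, but the protocol's two statements would still need aligning.

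Three stronger readings are tempting, and the documents do not support them:
- *Drug is never set against placebo.* Mean changes and SDs by arm are planned with a concurrent placebo group, so a reader could work out a difference. What is missing is a planned estimate with a bound.
- *Forty per arm is too few.* A 10 ms shift would be missed only 1% to 40% of the time at the assumed SDs, and the interval widths are usable. Triplicates also continue in all subjects until about 40 per arm complete, so more data may exist.
- *The sub-study will be reported as confirming no effect whatever happens.* The protocol contains no decision rule, so this is conjecture.

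On exposure, Section 3.2.1 says the doses were chosen for little overlap between arms, so the high-dose trough ECGs may inform on exposures in the lower-dose arms. That softens the trough limitation but does not remove the need to state it.

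**Conclusion.** The concern holds as a mismatch between aim and analysis. The protocol sets out to confirm no QT/QTc effect, and the QTc results "will be summarized descriptively by treatment group and visit" with category counts and shift tables. Without a placebo-corrected estimate and bound, an unremarkable table cannot carry that conclusion.

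The size of the gap depends on an SD that the protocol does not give. At 10 to 20 ms, the missing estimate would have a 90% CI half-width of about 3.7 to 7.4 ms at a single visit with 40 per arm. The 10 ms margin and the between-visit correlation of 0.5 are illustrations, not figures from the protocol. This is a secondary safety aim that should be corrected; it does not touch the primary efficacy result.

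**What to change.** In Section 4.8.5.3, with matching SAP text, add for each dose the placebo-corrected mean change from baseline in centrally read QTc (average of the triplicate). Take it from a repeated-measures model with baseline QTc as a covariate, and give two-sided 90% CIs.
- Prespecify one primary estimate per dose: either a single named visit or the average over on-treatment visits. Do not require the bound to clear the margin at every visit.
- Have the sponsor name the margin in advance. Claim no relevant effect only if the upper bound lies below it; otherwise report that an effect of that size is not excluded.
- Keep the category and shift tables as supportive displays.
- State that the ECGs in the two Q4W arms nominally fall four weeks after an active dose, so the conclusion applies to trough exposure.

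If the sponsor does not want a bounded claim, replace the aim in the synopsis, Section 3.1.1 and Section 4.3.3.4 with characterization.

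The cost is protocol and SAP wording plus one model on data already being collected. The downside is that with a large SD the bound may not clear the margin even for a drug with no effect, so the reported conclusion would be weaker than the current aim suggests.
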